2. LIST OF ABBREVIATIONS

ADR	Adverse Drug Reaction
AE	Adverse Event
AESI	Adverse Event of Special Interest
BD	Bronchodilator
BI	Boehringer Ingelheim
BP	Blood Pressure
CA	Competent Authority
CML	Local Clinical Monitor
COPD	Chronic Obstructive Pulmonary Disease
CRA	Clinical Research Associate
CRF	Case Report Form
CRO	Contract Research Organization
CTP	Clinical Trial Protocol
CTR	Clinical Trial Report
DMP	Data Management Plan
eCRF	Electronic Case Report Form
EDC	Electronic Data Capture
EU	European Union
EU PAS	European Union Post-Authorization Safety
EU-QPPV	European Union – Qualified Person for Pharmacovigilance
FDC	Fix Dose Combination
FEV ₁	Forced Expiratory Volume in one second
FVC	Forced Vital Capacity
GCP	Good Clinical Practice
GPP	Good Pharmacy Practice
IC50	Inhibitory Concentration
ICH	International Conference on Harmonisation
IEC	Independent Ethics Committee
IRB	Institutional Review Board
ISF	Investigator Site File
KNHANES	Korean National Health and Nutrition Examination Survey
LPVM	Local PV Manager

MAH	Marketing Authorisation Holder Activities
MedDRA	Medical Dictionary for Drug Regulatory Activities
MFDS	The Ministry of Food and Drug Safety
NCE	New Chemical Entity
NIS	Non-Interventional Study
NSADR	Non Serious Adverse Drug Reaction
OPU	Operative Unit
PASS	Post Authorization Safety Studies
PFT	Pulmonary Function Test
PMS	Post Marketing Surveillance
rNIS	Regulatory Non-Interventional Study
SADR	Serious Adverse Drug Reaction
SAE	Serious Adverse Event
SAP	Statistical Analysis Plan
SOP	Standard Operating Procedure
SUSAR	Suspected Unexpected Serious Adverse Reactions
TCM	Trial Clinical Monitor
TMF	Trial Master File
TMM	Team Member Medicine

3. RESPONSIBLE PARTIES

Boehringer Ingelheim(BI) has appointed a Trial Clinical Monitor(TCM), responsible for coordinating all required activities, in order to

- Manage the study in accordance with applicable regulations and internal standard operating procedures(SOPs).
- Direct the study team in the preparation, conduct, and reporting of the trial,
- Order the materials as needed for the study,
- Ensure appropriate training and information of Local Clinical Monitors(CMLs), Clinical Research Associate(CRAs), and Investigators of participating countries.

Data Management and Statistical Evaluation will be done by CRO according to CRO's SOPs.

The organization of the study in the participating countries will be done by the respective local BI- operative unit(OPU) or by a Contract Research Organization(CRO) with which the responsibilities and tasks will have been agreed and a written contract filed before initiation of the study. In each local BI OPU participating in this study, a CML will be appointed responsible for coordinating the activities required in order to manage the study in accordance with applicable regulations and internal SOPs in the countries covered by the respective BI OPU. On-site monitoring will be performed by BI or a CRO appointed by BI.

An Investigator Site File(ISF) containing all relevant study related documentation will be maintained according to local regulations and BI SOPs at each study site. A copy of the ISF documents will also be kept as an electronic Trial Master File(TMF) at BI according to BI SOPs. Documents related to participating physician and other important participants, especially their curricula vitae, will be filed in the TMF.

4. ABSTRACT

Name of company: [REDACTED]			
Name of finished medicinal product: Vahelva® Respimat®			
Name of active ingredient: Tiotropium + Olodaterol fixed-dose combination solution for inhalation - Respimat®			
Protocol date: 09 November 2016	Study number: 1237.60	Version/Revision: 2.0	Version/Revision date: 08 October 2020
Title of study:	A regulatory required non interventional study to monitor the safety and effectiveness of once daily treatment of orally inhaled Vahelva® Respimat® (Tiotropium + Olodaterol fixed dose combination 2.5µg/2.5µg per puff(2 puffs comprise one medicinal dose)) for Korean patients with COPD(Chronic Obstructive Pulmonary Disease)		
Rationale and background:	According to the local regulations, when a new chemical entity(NCE) is registered, a regulatory non interventional study(NIS) of an extended period(6 years) should be conducted. Such rNIS can provide supplementary data to monitor the safety of NCEs in a real-world situation. Data collected in randomized clinical study with strict inclusion/exclusion criteria and rigorous monitoring schemes have limitations.		
Research question and objectives:	To monitor the safety profile and effectiveness of Vahelva® Respimat® in Korean patients with COPD in a routine clinical practice setting		
Study design:	Observational prospective, non-interventional, open-label, multi-centre study		
Population:	
Patients diagnosed with COPD will be included.
 
Inclusion criteria:
 
• Patients who have been started on Vahelva® Respimat® in accordance with the approved label in Korea• Age \geq 18 years at enrolment• Patients who have signed on the data release consent form 
Exclusion criteria:
 
• Patients with hypersensitivity to Vahelva® Respimat® or to any of the excipients.• Patients with a history of hypersensitivity to atropine or its derivatives(e.g. ipratropium, oxitropium, glycopyrronium, aclidinium, umeclidinium)• Patients with asthma• Current participation in other clinical trials 
Patients for whom Vahelva® Respimat® is contraindicated according
		

Name of company: [REDACTED]					
Name of finished medicinal product: Vahelva® Respimat®					
Name of active ingredient: Tiotropium + Olodaterol fixed-dose combination solution for inhalation - Respimat®					
Protocol date: 09 November 2016	Study number: 1237.60	Version/Revision: 2.0	Version/Revision date: 08 October 2020		
local label of Vahelva® Respimat®.					
Variables:	Outcomes of safety All reported adverse events in patients who take at least once of Vahelva® Respimat® will be noted. Outcomes of effectiveness Change from baseline in (pre-dose) FEV ₁ , (Post Bronchodilator Predicted %) FEV1, mMRC scale after 24±2 weeks and/or 52±2 weeks, conditionally. And overall evaluation after 24±2 weeks and/or 52±2 weeks of treatment will be noted.				
Data sources:	Field study with new data collection				
Study size:	N=3,000 approximately Sample size of 3,000 patients is based on the requirement of the local regulatory authority (MFDS).				
Data analysis:	In this non-interventional study, all statistical analyses will be descriptive. Data of characteristics and other status of patients will be described and proportions including the confidence intervals will be provided.				
Milestones:	Study duration: 6 years (MFDS sets Vahelva® Respimat® re-examination period from 31 August 2015 to 30 Aug 2021. Interim report planned biannually for the initial two years and annually thereafter by November 2021.				

4.1 FLOW CHART

Data points	Baseline	Follow-up 1	Follow-up 2
Visit Number	1	2	3
Week/s	0	24±2	52±2
Informed consent	X		
Diagnosis	X		
Inclusion / exclusion criteria	X		
Demographics	X		
Medical history	X		
PFT value - FEV ₁ /FVC pred (%) - (Pre-dose) FEV ₁	X		
Physical examination	X	X	X
Concomitant medications	X	X	X
Vahelva® Respimat® administration status	X	X	X
(Pre-dose) FEV ₁	X	X ^A	X ^A
(Post Bronchodilator Predicted %) FEV ₁	X	X ^A	X ^A
Assessment of mMRC scale	X ^A	X ^A	X ^A
Laboratory data	X ^A	X ^A	X ^A
Adverse events		X	X
Study completion		X	X
Overall evaluation		X ^A	X ^A

A : If applicable

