9.2.3.2 Visit 1 - Baseline Visit

Upon patient enrolment, the following will be recorded on the patient's eCRF.

- Visit date
- Informed consent form: Date of Informed consent
- Diagnosis: Date of the diagnosis of COPD
- Inclusion / Exclusion criteria
- Demographic data: Initial, year of birth(age), gender, pregnancy, previous allergy, height, weight, smoking status
- Medical history: history of cardiovascular disease, metabolic disease, respiratory disease, any malignancy, renal dysfunction and other concomitant disease within 6 months.
- Physical examination: Blood pressure, pulse rate, body temperature
- PFT value for diagnosis of COPD: FEV₁/FVC predicted (%), (pre-dose) FEV₁ (within 6 months(180 days) prior to baseline date)
- Effectiveness outcomes : (pre-dose) FEV₁, (Post Bronchodilator Predicted %) FEV₁, mMRC scale(within 1 month(30 days) prior to baseline date)
- Concomitant medications: Record all medications have been taken at least once since one month(30 days) prior to the baseline visit.
- Dose of Vahelva® Respimat® given

At visit 1, the patient will be requested to contact the treating physician in the event of any adverse events noted after initiating Vahelva® Respimat® treatment.

9.2.3.3 Visit 2 - 24±2 weeks from Visit 1

After 24±2 weeks from Visit 1, the patients will return for follow-up. The followings will be noted and recorded in the eCRF.

- Visit date
- Physical examination: Blood pressure, pulse rate, body temperature
- Effectiveness assessment: (pre-dose) FEV₁, (post bronchodilator predicted %) FEV₁, mMRC scale
- Any change of Vahelva® Respimat® given
- Concomitant medications including new medications taken since last visit : any change in the concomitant medications(dose and dosing intervals)
- Any changes in laboratory tests if there is any lab result which was clinically significant compared to data before Vahelva® Respimat® therapy (This data is collected on the basis of medical need, i.e. independent of the NIS)
- Any adverse events noted
- Study completion status

- Overall evaluation
- NIS physician's electronic signature for data integrity(if applicable)

9.2.3.4 Visit 3 - 52±2 weeks from Visit 1

After 52±2 weeks from Visit 1, the patients will return for follow-up. The followings will be noted and recorded in the eCRF.

- Visit date
- Physical examination: Blood pressure, pulse rate, body temperature
- Effectiveness assessment: (pre-dose) FEV₁, post bronchodilator predicted %) FEV₁, mMRC scale

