9.3.2.2 Assessment of Effectiveness

- Post Bronchodilator Predicted % FEV1(Forced Expiratory Volume in one second): Post BD FEV1 should be collected within 1 month(30 days) prior to baseline and after 24 weeks and/or 52 weeks of treatment.
- (pre-dose) FEV₁ (Forced Expiratory Volume in one second): (pre-dose) FEV₁ should be collected within 1 month(30 days) prior to baseline and after 24 weeks and/or 52 weeks of treatment.
- mMRC scale: mMRC scale should be collected within 1 month(30 days) prior to baseline and after 24 weeks and/or 52 weeks of treatment.
- Overall evaluation: Overall evaluation will be assessed after 24 weeks or 52 weeks of treatment.

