9.3.4.1.5 Number of cases subject to effectiveness evaluation

These cases include those who signed the informed consent form to participate in this study as subject, visited as per the study schedule, took Vahelva® Respimat®, the cases included in safety evaluation, and were evaluated for the effectiveness including overall evaluation(if the case assessed as 'unassessable' will be excluded).

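### The flow chart makes the overall evaluation optional while the text requires it, so attending patients can leave the effectiveness rate unrated and uncounted

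*Combined protocol and SAP*

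**What the plan says.** The overall evaluation is described in five places.

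- **Flow chart (4.1).** The row carries superscript A at Visits 2 and 3, and the footnote reads "A : If applicable". Physical examination, adverse events and study completion have a plain X at the same two visits.
- **Abstract, Variables.** "And overall evaluation after 24±2 weeks and/or 52±2 weeks of treatment will be noted". No condition is attached. The preceding sentence, on FEV1 and mMRC, does end with one: "after 24±2 weeks and/or 52±2 weeks, conditionally".
- **Section 9.3.2.2.** "Overall evaluation will be assessed after 24 weeks or 52 weeks of treatment".
- **Visit 2 list (9.2.3.3).** The item "Overall evaluation" appears unqualified.
- **Visit 3 list (9.2.3.4).** The item does not appear.

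Section 9.3.2.1.2 turns the rating into a binary outcome: improved counts as effective, unchanged or aggravated as not. Section 9.7.4 plans an effectiveness rate with a 95% confidence interval.

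There are two entry rules. Section 9.3.4.1.5 takes cases that "were evaluated for the effectiveness including overall evaluation(if the case assessed as 'unassessable' will be excluded". Section 9.7 removes from the safety set only those without any effectiveness data or without COPD. Section 9.7.6 says that available data will be used and has no rule for an absent rating.

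**The concern.** The overall evaluation is a physician's judgement whose categories (9.3.3.7) are worded in terms of symptoms, and one category already covers insufficient information. It needs no test of its own. Yet a site working from the flow chart may treat it as optional, and a long-term site will not find it in its final-visit list.

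The rating is both the outcome and, under 9.3.4.1.5, the condition for entering the denominator. If physicians rate less readily when a patient has not done well, the denominator loses non-responders and the reported rate rises. The confidence interval reflects sampling error only and would not show this. The plan does characterise patients lost to follow-up (9.7.3, 9.9.1), but it does not do so for patients who attend and are not rated.

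**Working it through.** **Step 1: can the footnote be explained by the contracted term?** Each site contracts for either 24 or 52 weeks (9.5), so footnote A might mean no more than the follow-up that applies to that site. In that case adverse events and study completion would need the same mark, and they have a plain X at both follow-ups. The chart therefore conflicts with the abstract, 9.3.2.2 and the Visit 2 list.

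**Step 2: what happens to an attending patient with FEV1 but no rating?**
- Under 9.3.4.1.5 the patient is not an effectiveness case.
- Under 9.7 the patient is in the effectiveness set, because some effectiveness data exist. The patient still cannot be classed as effective or not effective, and no rule says how to count this.
- Safety cases (9.3.4.1.4) minus effectiveness cases (9.3.4.1.5) gives a total shortfall. That total mixes departures from the visit schedule, unrated patients and unassessable patients.
- Section 9.7.4.2 names the fourth category not applicable, where 9.3.2.1.2 has unassessable. Unrated and unassessable patients could be merged in the table.

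**Step 3: the plan's own figure.** The only size arithmetic is the long-term minimum in 9.5: 0.20 × 3,000 = 600, which reproduces. The 3,000 is a regulatory requirement without a formula. Neither figure bears on this point beyond setting N.

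**Step 4: illustration of size.** The documents give no expected effectiveness rate and no non-rating rate, so both are assumed. Let p be the true rate, s1 the share unrated among improvers and s0 the share unrated among the others. Take N = 3,000, all attending and none unassessable.

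Observed rate = p(1 − s1) / [p(1 − s1) + (1 − p)(1 − s0)]

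| p | s1 | s0 | Calculation | Observed | Shift (points) |
|---|---|---|---|---|---|
| 70% | 10% | 10% | 0.630/0.900 | 70.0% | 0 |
| 60% | 5% | 15% | 0.570/0.910 | 62.6% | +2.6 |
| 70% | 5% | 15% | 0.665/0.920 | 72.3% | +2.3 |
| 80% | 5% | 15% | 0.760/0.930 | 81.7% | +1.7 |
| 70% | 5% | 25% | 0.665/0.890 | 74.7% | +4.7 |
| 70% | 15% | 5% | 0.595/0.880 | 67.6% | −2.4 |

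In the third row 0.920 × 3,000 = 2,760 patients are rated. The 95% half-width is 1.96 × √(0.723 × 0.277 / 2,760) = 1.7 points, so a shift of 2.3 points exceeds what the interval conveys.

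**Step 5: what the proposed reporting would show.** In that row 8% are unrated. Counting them all as not effective gives 0.665, or 66.5%; counting them all as effective gives 0.665 + 0.080 = 74.5%. The true 70% lies between. The width of this range equals the unrated share whatever the mechanism, which is why the count itself is the useful number.

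**The case against.** The strongest reply is that three places state the overall evaluation without condition and only a chart footnote says otherwise. A reader might infer that the plan lets investigators skip the rating. The documents do not settle that; they contradict each other, and the defect is the contradiction.

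A reader might also extend the point to mMRC, which carries the same footnote. That is not supported. mMRC does not decide who enters the rate, and the abstract makes it conditional in terms: "mMRC scale after 24±2 weeks and/or 52±2 weeks, conditionally". Section 9.3.2.2 is firmer ("mMRC scale should be collected within 1 month(30 days) prior to baseline and after 24 weeks and/or 52 weeks of treatment"), but mMRC entered with the amendment of 17 September 2020, while data collection runs from 30 July 2016 to 30 August 2021 (section 6). Patients enrolled before the amendment have a baseline mMRC only if it was recorded in routine care. A patient enrolled on the amendment date reaches week 50, the earliest Visit 3, on 2 September 2021, after collection ends.

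Three further objections have weight.

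- The rating draws partly on FEV1 and mMRC change (9.3.2.1.2), which may be missing at follow-up. The unassessable category already exists for that case.
- Requiring the rating does not stop exclusions, because an investigator can still enter unassessable. The change makes exclusions visible; it does not remove them.
- Section 9.7 refers details to a SAP, and a rule for unrated patients could stand there. The text available contains none.

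The consequence is also limited. Safety is the primary objective, FEV1 is the main effectiveness outcome, this rating is listed among other outcomes, and all analyses are descriptive.

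**Conclusion.** The point holds for the overall evaluation only. The flow chart conflicts with three other places, the Visit 3 list omits the item, and the two entry rules treat an unrated patient differently. As written, the effectiveness rate is open to selective non-rating, and no count is planned that would show it.

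The size is unknown. A reader might take the illustration as evidence that the rate will be overstated by some points; it is not. Under the assumed patterns the shift runs from −2.4 to +4.7 points at a true 70%, and equal skipping gives none. What does follow from the documents is that the reader could not tell which case applies. This is an inexpensive improvement to a secondary, descriptive result and does not threaten the study's main purpose.

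**What to change.** 1. In the flow chart, remove footnote A from the overall evaluation row. Require the rating at the patient's final follow-up, 24 or 52 weeks as contracted, with unassessable plus a reason as the only alternative. This fits 9.3.2.1.2 and 9.3.2.2, which ask for one time point or the other; a rating at every attended visit would go beyond them.
2. Add the item to the Visit 3 list in 9.2.3.4.
3. Align 9.3.4.1.5 with 9.7 so that one rule defines the denominator, and use one name for the fourth category in 9.3.2.1.2 and 9.7.4.2.
4. Report the number unrated and the number unassessable beside the effectiveness rate, separately for short-term and long-term patients. Add a sensitivity rate counting both groups as not effective. For patients whose final visit has passed, this reporting is the part that can still be applied.
5. Leave mMRC, follow-up spirometry and laboratory data conditional.

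The cost is one rating per patient, an eCRF completeness check and a table line. The sensitivity figure will be somewhat less favourable than the main rate and should be labelled as a lower bound: in the illustration it reads 66.5% against a true 70%. No test is added to routine care.

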5. AMENDMENTS AND UPDATES

Number	Date	Section of study protocol	Amendment or update	Reason
2	17 September 2020	9.2.3.2 visit 1 – Baseline visit	Effectiveness outcomes: (pre-dose) FEV1, BDI(within 1 month(30 days) prior to baseline date) Was changed to: Effectiveness outcomes: (pre-dose) FEV1, (Post Bronchodilator Predicted %) FEV1, mMRC scale(within 1 month(30 days) prior to baseline date)	Reflect to HA's feedback and epidemiology team's feedback
2	17 September 2020	9.2.3.3 Visit 2 - 24±2 weeks from Visit 1	Effectiveness assessment: (pre-dose) FEV1, TDI Was changed to: Effectiveness assessment: (pre-dose) FEV1, (post bronchodilator predicted %) FEV1, mMRC scale	Reflect to HA's feedback and epidemiology team's feedback
2	17 September 2020	9.2.3.4 Visit 3 - 52±2 weeks from Visit 1	Effectiveness assessment: (pre-dose) FEV1, TDI Was changed to: Effectiveness assessment: (pre-dose) FEV1, (post bronchodilator predicted %) FEV1, mMRC scale	Reflect to HA's feedback and epidemiology team's feedback
2	17 September 2020	9.3.2.1.1 Main outcome	Change from baseline in (pre-dose) FEV1 after 24 weeks and/or 52 weeks of treatment Was changed to: Change from baseline in (Post Bronchodilator Predicted %) FEV1 after 24 weeks and/or 52 weeks of treatment	Reflect to HA's feedback and epidemiology team's feedback
2	17 September	9.3.2.1.2 Other	Change from baseline in TDI after 24 weeks and/or 52	Reflect to HA's feedback and

	2020	outcomes	weeks of treatment Was changed to: Change from baseline in Pre-dose FEV1 after 24 weeks and/or 52 weeks of treatment Change from baseline in mMRC score after 24 weeks and/or 52 weeks of treatment	epidemiology team's feedback
2	17 September 2020	9.3.2.2 Assessment of Effectiveness	
 • (pre-dose) FEV1 (Forced Expiratory Volume in one second): (pre-dose) FEV1 should be collected within 1 month(30 days) prior to baseline and after 24 weeks and/or 52 weeks of treatment. • BDI/TDI(Baseline Dyspnea Index/Transition Dyspnea Index): BDI/TDI should be collected within 1 month(30 days) prior to baseline and after 24 weeks and/or 52 weeks of treatment. • Overall evaluation: Overall evaluation will be assessed after 24 weeks or 52 weeks of treatment. Was changed to: 
 • Post Bronchodilator Predicted % FEV1(Forced Expiratory Volume in one second): Post BD FEV1 should be collected within 1 month(30 days) prior to baseline and after 24 weeks and/or 52 weeks of treatment. • (pre-dose) FEV₁ (Forced Expiratory Volume in one second): (pre-dose) FEV₁ should be collected within 1 month(30 days) prior to baseline and after 24 weeks and/or 52 weeks of treatment. 	Reflect to HA's feedback and epidemiology team's feedback

			
treatment.
 
• mMRC scale: mMRC scale should be collected within 1 month(30 days) prior to baseline and after 24 weeks and/or 52 weeks of treatment.• Overall evaluation: Overall evaluation will be assessed after 24 weeks or 52 weeks of treatment.	
--	--	--	--	--

6. MILESTONES

Milestone	Planned Date
Start of data collection	30 Jul 2016
End of data collection	30 Aug 2021
Interim report 1	30 Apr 2016
Interim report 2	30 Oct 2016
Interim report 3	30 Apr 2017
Interim report 4	30 Oct 2017
Interim report 5	30 Oct 2018
Interim report 6	30 Oct 2019
Interim report 7	30 Oct 2020
Registration in the EU PAS register	29 Aug 2016
Final report of study results:	30 Nov 2021

7. RATIONALE AND BACKGROUND

7.1 RATIONALE

According to the local regulations, when a new chemical entity(NCE) is registered, a regulatory non interventional study(NIS) of an extended period(6 years) should be conducted. Such rNIS can provide supplementary data to monitor the safety of NCEs in a real-world situation. Data collected in randomized clinical study with strict inclusion/exclusion criteria and rigorous monitoring schemes have limitations.

This is an open-label, multi-centre and national non-interventional study based on newly collected data. It will provide additional safety information of Vahelva® Respimat® (Tiotropium + Olodaterol) in Korean patients with COPD(Chronic Obstructive Pulmonary Disease) in a routine clinical practice setting.

